#### **4.1.6. Supplementary Analysis**

The following plots will be created and will include urinary bladder  $SUV_{mean}$  among other normal organs:

- Violin plots of  $SUV_{mean}$  by normal organs for piflufolastat (18F) and flotufolastat (18F). All organs will be assessed for normality via. histograms and Q-Q plots. For data assessed to be normally distributed the mean with STD error will be presented. For data assessed to be not normally distributed, the median and interquartile range will be presented. This will be summarised for all patients in the EAS.

## 5. Analyses Supporting Secondary Objectives

### 5.1. Secondary Endpoint 1

To assess the detection rates for piflufolastat (18F) PET and flutufolastat (18F) PET.

#### 5.1.1. Definition of Secondary Endpoint 1

The patient-level detection rate for piflufolastat (18F) PET and flutufolastat (18F) PET is defined as:

$$\frac{\text{Patients with positive lesions}}{\text{Total number of patients}}$$

#### 5.1.2. Analytical Approach for Secondary Endpoint 1

The frequency of positive lesions, detection rates and corresponding 95% exact CI will be calculated for piflufolastat (18F) PET and flutufolastat (18F) PET for each blinded reader, and the overall adjudicated result (see [Section 2.10](#)). For each blinded reader, the number of positive reads that were adjudicated will also be summarised. A shift table comparison of positive and negative lesions will also be presented for each blinded reader, and the overall adjudicated result. The EAS will be used, and the detection rate table will be repeated for the FAS.

### 5.2. Secondary Endpoint 2

To assess the detection rates stratified by PSA level for piflufolastat (18F) PET and flutufolastat (18F) PET.

#### 5.2.1. Definition of Secondary Endpoint 2

The first grouping for the PSA stratification will be as follows:

- PSA  $\leq 0.2$
- PSA  $> 0.2$

The second grouping for the PSA stratification will be as follows:

- PSA  $\leq 0.2$
- $0.2 < \text{PSA} \leq 0.3$
- $0.3 < \text{PSA} \leq 0.4$
- $0.4 < \text{PSA} \leq 0.5$

Any PSA subgroup with fewer than 5 patients will be grouped with the adjacent PSA subgroup with the smallest number of patients. If a PSA value is reported as “< X”, i.e. below the lower limit of quantification, the value will be converted to X for summaries, but will be presented as recorded, i.e. as “< X” in the listings.

See [Section 5.1.1](#) for the definition of detection rate.

### **5.2.2. Analytical Approach for Secondary Endpoint 2**

The analysis for the patient-level detection rates stratified by PSA level will be performed using the same approach as the patient-level detection rates specified in [Section 5.1.2](#). In addition, bar charts of patient-level detection rates by each PSA group will also be presented.

## **5.3. Secondary Endpoint 3**

To assess the detection rates for local recurrences in the prostate bed for piflufolastat (18F) PET and flutufolastat (18F) PET for the following subregions:

- Vesicourethral anastomosis lesions.
- Retrovesical lesions.
- Remnant seminal vesicles/lateral surgical margin lesions.

If either side (left or right) of the remnant seminal vesicles/lateral surgical margin is positive, then remnant seminal vesicles/lateral surgical margin lesions will be classed as positive.

### **5.3.1. Definition of Secondary Endpoint 3**

See [Section 5.1.1](#) for the definition of detection rate.

### **5.3.2. Analytical Approach for Secondary Endpoint 3**

The analysis for the detection rates for local recurrences by subregion will be performed using the same approach as the patient-level detection rates specified in [Section 5.1.2](#).

## **5.4. Secondary Endpoint 4**

To assess the PLN detection rates for piflufolastat (18F) PET and flutufolastat (18F) PET.

### **5.4.1. Definition of Secondary Endpoint 4**

See [Section 5.1.1](#) for the definition of detection rate.

If either side (left or right) of the PLN is positive, then PLN will be classed as positive.

### **5.4.2. Analytical Approach for Secondary Endpoint 4**

The analysis for the detection rates for PLNs will be performed using the same approach as the patient-level detection rates specified in [Section 5.1.2](#).

## **6. Analyses Supporting Tertiary Objective(s)**

### **6.1. Tertiary Endpoint 1**

To assess the central reader qualitative assessment of the presence or absence of ureteric radioactivity in piflufolastat (18F) PET and flutufolastat (18F) PET.

#### **6.1.1.1. Definition of Tertiary Endpoint 1**

The qualitative assessment will be assigned by each blinded reader and will be defined as:

- Absent
- Present

#### **6.1.1.2. Analytical Approach for Tertiary Endpoint 1**

The number and percentage of patients with the presence or absence of ureteric radioactivity for piflufolastat (18F) PET and flotufolastat (18F) PET will be summarized for each blinded reader, and the overall adjudicated result (see [Section 2.10](#)). The FAS will be used.

### **6.2. Tertiary Endpoint 2**

To assess bladder  $SUV_{max}$ , bladder  $SUV_{peak}$  and total bladder radioactivity for piflufolastat (18F) PET and flotufolastat (18F) PET.

#### **6.2.1.1. Definition of Tertiary Endpoint 2**

See [Section 4.1.1](#) for the definition of difference in SUV.

#### **6.2.1.2. Analytical Approach for Tertiary Endpoint 2**

The analysis for  $SUV_{max}$ ,  $SUV_{peak}$  and total bladder radioactivity will be performed using the same approach as the primary analysis specified in [Section 4.1.1](#). The supplementary analysis specified in [Section 4.1.6](#) will also be repeated for  $SUV_{peak}$ .

### **6.3. Tertiary Endpoint 3**

To assess  $SUV_{mean}$  and  $SUV_{peak}$  in normal organs for piflufolastat (18F) PET and flotufolastat (18F) PET.

#### **6.3.1.1. Definition of Tertiary Endpoint 3**

See [Section 4.1.1](#) for the definition of difference in SUV.

For the kidneys, lacrimal glands, parotid glands and the sub-mandibular glands where biodistribution is measured on the left and right sides, the average will be calculated and summarised.

#### **6.3.1.2. Analytical Approach for Tertiary Endpoint 3**

The analysis for  $SUV_{mean}$ ,  $SUV_{peak}$  in normal organs will be performed using the same approach as the primary analysis specified in [Section 4.1.1](#).

## 6.4. Tertiary Endpoint 4

To assess the detection rates for distant metastatic lesions for piflufolastat (18F) PET and flutufolastat (18F) PET and for the following subregions:

- Bone lesions.
  - Bone lesions (Pelvis).
  - Bone lesions (Spine).
  - Bone lesions (Ribs).
  - Bone lesions (Other).
- Extra-pelvic lymph node lesions.
- Extra-pelvic soft tissue lesions.

For bone lesions, any positive bone subregion would class as positive for bone lesions.

### 6.4.1.1. Definition of Tertiary Endpoint 4

See [Section 5.1.1](#) for the definition of detection rate.

### 6.4.1.2. Analytical Approach for Tertiary Endpoint 4

The analysis for the detection rates for distant metastatic lesions and by subregion will be performed using the same approach as the patient-level detection rates specified in [Section 5.1.2](#).

## 6.5. Tertiary Endpoint 5

To assess the qualitative 3-point scale by expert readers for piflufolastat (18F) PET and flutufolastat (18F) PET.

### 6.5.1.1. Definition of Tertiary Endpoint 5

Blinded readers will qualitatively assess the impact of any urinary activity in the bladder on image interpretation using a three-point scale:

0 = No/minimal visible urinary activity.

1 = Urinary activity visible but distinction between urine and disease possible.

2 = Assessment inhibited by urinary activity.

### 6.5.1.2. Analytical Approach for Tertiary Endpoint 5

The frequency and percentage of each score will be calculated for piflufolastat (18F) PET and flutufolastat (18F) PET for each blinded reader, and the overall adjudicated result (see [Section 2.10](#)). A separate summary of scores 0 and 1 combined will also be summarised. Shift tables for each reader, and the overall adjudicated result will also be presented.

Patient-level detection rates will also be summarised, stratified by 0 or 1, and 2 for each blinded reader, and the overall adjudicated result.

The FAS will be used.

## 7. Safety Analyses

Safety analyses include extent of exposure and AEs. All safety analyses will be performed on the SAF.

### 7.1. Extent of Exposure

A summary of total administered activity will be provided. All activity will be shown in MBq and mCi using the conversion 1 mCi=37 MBq. Exposure will be summarized for piflufolastat (18F) and flotufolastat (18F).

Doses outside the acceptable ranges will also be summarised:

- Acceptable range for Piflufolastat: Total administered activity 296 MBq to 370 MBq (8 to 10 mCi)
- Acceptable range for Flotufolastat: Total administered activity 236.8 MBq to 355.2 MBq (6.4 to 9.6 mCi)

### 7.2. Adverse Events

A TEAE is defined as an AE that started or worsened after administration of piflufolastat up to the final safety monitoring telephone call after the administration of flotufolastat (18F) (Visit 4). All AE verbatim terms will be coded by system organ class (SOC) and preferred term (PT) using Medical Dictionary for Regulatory Activities (MedDRA) version 26.1 or higher. TEAEs will be summarized overall and categorized by those attributable to piflufolastat and those attributable to flotufolastat, as described in

[Table 3](#).

**Table 3 Treatment-Emergent Adverse Event Definitions**

Time Period	Categorization

AEs occurring from the time of administration of piflufolastat (18F) (Scan 1; Visit 2) to the earliest of either:
 
 
• One day after administration of piflufolastat (18F)
 
• The time of administration of flotufolastat (18F) (Scan 2; Visit 3).
 
 
Note: AEs occurring at the time of flotufolastat will not be attributable to piflufolastat (18F).
	Attributable to piflufolastat (18F)

AEs occurring from the time of administration of flotufolastat (18F) (Scan 2; Visit 3) to the earliest of either:
 
 
• One day after administration of flotufolastat (18F)
 
• Final safety monitoring telephone call after the administration of flotufolastat (18F) (Visit 4)
 
 
AEs that are considered related to flotufolastat (18F) will also be assigned attributable to flotufolastat (18F).
	Attributable to flotufolastat (18F)

The tables will include the number and percentage of patients reporting any event of that term and the total number of events reported.

An overview of TEAEs table will be produced and will include the following categories:

- TEAEs
- TEAEs related to flutufolastat (18F)
- TEAEs by Common Terminology Criteria for Adverse Events (CTCAE) grade
  - Individually by maximum grade
  - Any Grade  $\geq 3$
- Treatment-emergent serious adverse events (TESAEs)
- TESAEs related to flutufolastat (18F)
- TESAEs resulting in death

The following is a list of summary tables that will also be generated:

- TEAEs by SOC and PT
- TEAEs by descending order of frequency of PT
- TEAEs related to flutufolastat (18F) by SOC and PT
- TEAEs by Maximum CTCAE grade, SOC, and PT
- TESAEs by SOC and PT
- TESAEs related to flutufolastat (18F) by SOC and PT
- TESAEs resulting in death by SOC and PT

For each category and overall, patients reporting more than 1 occurrence for a term (SOC or PT) will be counted only once using the most extreme event (most severe for CTCAE tables).

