12 ADVERSE EVENT REPORTING AND DOCUMENTATION

12.1 Adverse Events

An AE is any untoward medical occurrence in a clinical investigation of a patient administered a pharmaceutical product and that does not necessarily have a causal relationship with the product. An AE is therefore any unfavorable and unintended sign (including an abnormal laboratory finding, if applicable), symptom or disease temporally associated with the administration of a pharmaceutical product, whether or not related to that product. An unexpected AE is one of a type not identified in nature, severity, or frequency in the USPI, or of greater severity or frequency than expected based on the information in the USPI.

The collection period for all AEs will begin after informed consent is obtained and end after procedures for the final study visit have been completed (i.e., post-procedural safety monitoring telephone call 24 hours after the flutufolastat (^{18}F) PET scan [Visit 4]). AEs will be assigned as treatment-emergent or non-treatment-emergent as outlined in [Table 2](#).

Table 2: Treatment-emergent Adverse Event Definitions

Time Period	Categorization

 AEs occurring after informed consent (Visit 1) but prior to administration of piflufolastat (^{18}F) (Scan 1; Visit 2) 	
 Non-treatment-emergent

 AEs occurring from the time of administration of piflufolastat (^{18}F) (Scan 1; Visit 2) to the time of administration of flutufolastat (^{18}F) (Scan 2; Visit 3) 	
 Treatment-emergent: attributable to piflufolastat (^{18}F) 
Note: any TEAEs attributable to piflufolastat (^{18}F) will not be assigned causality (related/not related to piflufolastat (^{18}F))

 AEs occurring from the time of administration of flutufolastat (^{18}F) (Scan 2; Visit 3) to the final post-flutufolastat (^{18}F) PET safety monitoring telephone call (Visit 4) 	
 Treatment-emergent: attributable to flutufolastat (^{18}F)

Abbreviations: ^{18}F =fluorine-18; AE=adverse event; PET=positron emission tomography.

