## 1.2. Study Design

This is a multi-center, prospective intra-patient comparator study of urinary radioactivity SUV following both piflufolastat (18F) and flotufolastat (18F) PET in patients with low PSA ( $\leq 0.5$  ng/mL) biochemical recurrence (BCR) of prostate cancer following radical prostatectomy (RP). Approximately 60 patients will be screened for inclusion into the study to obtain a minimum of 52 evaluable patients (i.e. have evaluable PET scans for both piflufolastat (18F) and flotufolastat (18F) available for analysis). As part of their routine clinical care, each patient will be administered a single dose of piflufolastat (18F) on Day 1, followed by a PET scan per standard institutional practice and in line with the PYLARIFY United States Prescribing Information (USPI) (PYLARIFY® [piflufolastat F 18] injection USPI, 2021.). At least 24 hours after the piflufolastat (18F) scan, but within 10 calendar days, all patients will be administered a single dose of flotufolastat (18F) followed by a PET scan. Each patient will receive both radiopharmaceuticals and, thus, serve as their own control.

For the primary endpoint analysis, volumes of interest (VOIs) will be placed over the urinary bladder and radioactivity (SUV metrics) will be assessed following administration of each radiopharmaceutical.

For secondary and tertiary endpoints, both the piflufolastat (18F) and flotufolastat (18F) PET scans will be read by two independent nuclear medicine physicians or nuclear radiologists who are blinded to the patient's clinical history but have been trained to read scans for each respective radiopharmaceutical using product-specific training and in line with the respective FDA-approved USPI for the respective radiopharmaceutical. To facilitate use of the appropriate product-specific training, the independent

readers will be unblinded to the administered agent. Any image interpretation disagreements will be resolved by a third independent adjudicator. Full details are in the Study Image Review Charter.

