#### 2.4.4. Causality and Severity

For AEs, if causality is missing then the AE will be assumed to be related. If the severity is missing, the AE will be assumed to be Grade 3.

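### SAP Table 3 leaves treatment-emergent adverse events between the two one-day tracer windows in neither category, with no declared change from the protocol, and the missing-causality rule has no onset condition

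*SAP*

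**What the plan says.** **Attribution windows.** In protocol Section 12.1, Table 2, the piflufolastat category covers "AEs occurring from the time of administration of piflufolastat (^{18}F) (Scan 1; Visit 2) to the time of administration of" flotufolastat, with no other limit. In SAP Section 7.2, Table 3, the same category ends at the earlier of two limits: the flotufolastat injection, or "One day after administration of piflufolastat (18F"). The flotufolastat window opens at its own injection and closes at the earlier of one day or the Visit 4 call.

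**What counts as treatment-emergent.** SAP 7.2 uses one continuous period: "A TEAE is defined as an AE that started or worsened after administration of piflufolastat up to the final safety monitoring telephone call". It then summarises these events overall and by tracer. The gap between tracers is "At least 24 hours after the piflufolastat (18F) scan, but within 10 calendar days"; protocol Table 1 places Scan 2 on Days 2 to 10.

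**Declared changes.** SAP Section 1 says the SAP overrides the protocol and that changes are described in Section 10. Section 10 reads as not applicable.

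**Causality.** Protocol Table 2 says of piflufolastat-period events that they "will not be assigned causality (related/not related to piflufolastat"). Protocol 12.3 repeats this, then has the relationship of an adverse event to flotufolastat graded on Table 5, which includes an unrelated category and states no onset limit. SAP 2.4.4 says: "For AEs, if causality is missing then the AE will be assumed to be related". It names no tracer and sets no onset condition. SAP Table 3 adds that events considered related to flotufolastat "will also be assigned attributable to" flotufolastat, again without a timing condition.

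**The concern.** The safety endpoint (protocol 5.4; SAP Table 1) is the incidence of treatment-emergent events after each scan, and protocol 15.5 promises a summary for each tracer. The by-tracer split is therefore the endpoint itself. If SAP Table 3 assigns some treatment-emergent events to no tracer, the piflufolastat figure is not the one the protocol defines, and a reader of the report would find no declared change to explain the difference.

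The causality rule raises a separate risk. Flotufolastat is the only tracer with relatedness tables. An imputation rule that ignores onset could place in those tables an event that began before flotufolastat was given.

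**Working it through.** The plan states no figure on this point. The check is a comparison of windows, plus simple arithmetic on the time covered.

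**1. Uncovered time between tracers.** Inputs: piflufolastat on Day 1; Scan 2 on Day d, with d from 2 to 10 (protocol Table 1); SAP piflufolastat window of one day at most (SAP Table 3). In whole days:

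- interval between injections = d − 1
- covered by SAP Table 3 = min(1, d − 1)
- uncovered = (d − 1) − min(1, d − 1)

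| Scan 2 on | Interval (days) | Covered | Uncovered | Share uncovered |
|---|---|---|---|---|
| Day 2 | 1 | 1 | 0 | 0% |
| Day 3 | 2 | 1 | 1 | 50% |
| Day 5 | 4 | 1 | 3 | 75% |
| Day 7 | 6 | 1 | 5 | 83% |
| Day 10 | 9 | 1 | 8 | 89% |

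Under protocol Table 2 the uncovered time is 0 on every row. The documents give no distribution of Scan 2 days. If Scan 2 were spread evenly over Days 2 to 10 (an assumption), the mean interval would be 45/9 = 5.0 days and the mean uncovered time 36/9 = 4.0 days, or 80%.

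**2. Where a gap event goes.** Take an event starting on Day 5 in a patient scanned with flotufolastat on Day 10.

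- SAP 7.2: treatment-emergent, so it is in the overall summary.
- SAP Table 3, piflufolastat row: outside, because more than one day has passed.
- SAP Table 3, flotufolastat row, by time: outside, because flotufolastat has not been given.
- Protocol Table 2: attributable to piflufolastat.

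The partial-date rule in SAP 2.4.2 gives a different answer again. If the day of that event were missing, and its month and year matched both injections, it would be attributed to both tracers. With a full date it falls in neither window.

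**3. The causality rule for the same event.** The result depends on how the flotufolastat causality field is filled in, which the documents do not show.

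- Recorded as unrelated: SAP 2.4.4 does not apply and the event stays in neither window.
- Blank: SAP 2.4.4, read literally, makes it related. Since relatedness is tabulated only for flotufolastat, it would enter the flotufolastat-related tables.
- Blank, and an imputed value also counts as considered related in Table 3: the event becomes attributable to flotufolastat instead of to neither tracer.

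The last outcome and the neither-tracer outcome are alternatives for a given event. Both differ from protocol Table 2.

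**The case against.** **The one-day window is defensible.** Flotufolastat follow-up ends with a telephone call about 24 hours after Scan 2, so equal one-day windows compare like with like, whereas the protocol windows could set up to 9 days against about 1. Protocol Section 15 also allows the SAP to modify planned analyses. This stands. The fault is not the length of the window but that the change is undeclared and leaves a set of treatment-emergent events without a category.

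**Nothing is lost.** Gap events remain in the overall summary and the adverse event listing. Patients are counted once per category and once overall, so patient counts by tracer need not add to the total in any case. This also stands; the loss is confined to the by-tracer split.

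**Days are not events.** Eight of nine days is the extreme, and with Scan 2 on Day 2 the gap is zero. Events after piflufolastat are not solicited (protocol 12.1), and no event rate is given. A reader might infer that most piflufolastat events go unattributed; the documents do not support that.

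**The causality problem may never arise.** A reader might infer that every event before flotufolastat is bound to be reported as related to it, on the ground that causality is withheld by design. That goes too far. What the protocol withholds is relatedness to piflufolastat. Protocol 12.3 has relatedness to flotufolastat assessed without an onset limit, so a site can record an earlier event as unrelated. Table 3's reference to events considered related most naturally means an investigator's judgement, not an imputed value. Events before piflufolastat are not treatment-emergent, so they cannot enter these tables. What remains is that nothing in SAP 2.4.4 stops a blank from being imputed as related when onset precedes the drug.

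**Conclusion.** The window point holds on the text. SAP Table 3 is narrower than protocol Table 2, the difference is not declared in Section 10, and treatment-emergent events between the windows belong to neither tracer by time. In whole days the uncovered time runs from 0 of 1 to 8 of 9, depending on the day of Scan 2. The count of events cannot be derived from the documents.

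The causality point holds only conditionally. It needs a blank flotufolastat causality field for an event with onset before flotufolastat, and a literal application of SAP 2.4.4. Attribution to flotufolastat needs a further step: that an imputed value triggers the last sentence of Table 3.

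The safety analysis is descriptive and the primary endpoint is untouched. The correction is still worth making, because it concerns a stated endpoint and costs very little.

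**What to change.** 1. **SAP Table 3 and Section 10.** Either restore the protocol Table 2 window, or keep the equal one-day windows, add a row labelled *treatment-emergent, between tracer windows*, and declare the change in Section 10.
2. **SAP 2.4.4.** Limit the missing-causality rule to adverse events with onset at or after flotufolastat administration. Show earlier events with no recorded causality as *causality not assessed*.

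The cost is about two sentences and one table row, with matching edits to the table shells. No new data are needed. The change should be made before database lock, so that the categories are fixed before the events are tabulated.
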